4.0	10/18/22	
 -Addition of vital measurements pre/post stimulation sessions 2-5 -Box and blocks test and adverse event survey will now also be during session 2 as it is during 3-5 -Addition of new recruitment strategies -clarification of intellectual disability population - removal of device log which is not needed - clarification of screening procedures and inclusion of more parental demographic information -potential for more than one study monitor in the home 	
 -Increase safety of participant by monitoring vitals throughout and motor function and adverse events even during sham stimulation -Other changes were to clarify procedures already approved - added additional recruitment measures to ensure we could enroll enough participants in the short timeframe we have - ensuring safety for the study monitors
5.0	12/14/22	
 - Adding MRI screening visit - Adding AE surveys to Session Day 1 - Adding a therapy questionnaire 	
 - Adding AE surveys to Day 1 will give us good baseline information for whether just wearing the device without stimulation affects the subject - Previously we have discussed acquiring information but did not have a formal survey for assessing this information
6.0		Expanding age range to 21 years	
7.0	3/23/23	Allow participation from participants 18-21 who have a legally authorized representative and lack the capacity to consent to study participation	

8.0	5/4/23	
-Changing funding source-Adding an optional 6 month follow up study	Allows us to follow up on the health and motor function of individuals who participated in receiving tDCS stimulation in this study
------------	--------	--	---

Table of Contents

1.0 STATEMENT OF COMPLIANCE.....	1
2.0 LIST OF ABBREVIATIONS.....	2
3.0 STUDY SUMMARY.....	3
3.1 Synopsis.....	3
3.2 Schematic of Study Design.....	5
4.0 KEY ROLES.....	6
5.0 INTRODUCTION.....	7
5.1 Cerebral Palsy and Motor Rehabilitation.....	7
5.2 Investigational Procedure.....	7
5.3 Rationale.....	7
6.0 STUDY OBJECTIVES AND ENDPOINTS.....	8
6.1 Aims.....	8
7.0 STUDY DESIGN.....	9
7.1 General Design.....	9
7.2 End of Study Definition.....	9
8.0 SUBJECT SELECTION	9
8.1 Inclusion & Exclusion Criteria.....	9
8.2 Vulnerable Populations	10
8.3 Lifestyle Considerations	12
8.4 Subject Identification	12
8.4.1 Self-Identification	12

2.0 LIST OF ABBREVIATIONS

AE	Adverse Event
CFR	Code of Federal Regulations
CP	Cerebral Palsy
C-PROGRESS	Center for Pediatric Rehabilitation: Growing Research, Education, and Sharing Science
CTMS	Clinical Trial Management Software
DHHS	Department of Health and Human Services
DSMC	Data & Safety Monitoring Committee
DSMP	Data & Safety Monitoring Plan
FDA	Food and Drug Administration
GCP	Good Clinical Practice
HIPAA	Health Insurance Portability and Accountability Act
IDE	Investigational Device Exemption
ICTR	Institute for Clinical and Translational Research
IND	Investigational New Drug Application
IRB	Institutional Review Board
MRI	Magnetic Resonance Imaging
NIH	National Institutes of Health
OHRP	Office for Human Research Protections
OnCore	Online Collaborative Research Environment
PI	Principal Investigator
REDCap	Research Electronic Data Capture
SAE	Serious Adverse Event
SMC	Safety Monitoring Committee
SMP	Study Monitoring Plan
tDCS	Transcranial Direct Current Stimulation
UP	Unanticipated Problem
UP	Unanticipated Problem

[figure not shown]
3.0 STUDY SUMMARY

3.1 Synopsis

Full Title	Remotely Monitored Transcranial Direct Current Stimulation in Children with Cerebral Palsy
Short Title	Pediatric Brain and Movement
Protocol Number	[HS IRB]
ClinicalTrials.gov Identifier & Summary	This study is being performed to determine the safety, tolerability and feasibility of remotely monitored transcranial direct current stimulation for children with cerebral palsy.
Number of Site(s)	This study is being done at one site: The University of Wisconsin Madison.
Main Inclusion Criteria	
 Children with hemiparetic cerebral palsy with a radiologically confirmed perinatal brain bleed/stroke Ability to follow 2-step commands Aged between 8 years 0 days and 21 years.
Main Exclusion Criteria	
 Inaccessibility to internet and a working computer/laptop/device Neoplasm Presence of metal implants Epilepsy History of seizure within 2 years preceding the study
Objective(s)	
Primary Objective
 
 To assess safety and tolerability of remotely monitored tDCS using our safety survey and optional 6-month/12-month follow up 
Secondary Objectives
 
 To evaluate the quality, ease and comfort of in-home device set-up. To evaluate the quality of tDCS stimulation.
Endpoints	
Primary Endpoint
 
Adverse events survey (pre, during, and post stimulation on sessions 1-5) and Box and Blocks test (pre and post stimulation sessions 2-5) will assess possible adverse effects.
 
Secondary Endpoints
 
 Setup speed SMARTscan™ electrode contact quality
Study Design	This is an exploratory pilot open label trial that will assess the safety and feasibility of active tDCS in the home setting under caregiver and remote investigator supervision and direction, with a study safety monitor in the home on days when there is an active device present. An optional 6 month/12-month follow up session will be completed to to assess Box and Blocks scores and medical status since r participation in the primary study.

IND or IDE Number	Abbreviated IDE requirements apply for Non-Significant Risk Device
Study Intervention	Participants will receive 20 minutes of 1.5 mA transcranial direct current stimulation (tDCS) for three consecutive days.
Total Number of Subjects	A total of 10 subjects will be recruited.
Study Population	Male and females aged 8 to 21 with established diagnosis of hemiparetic cerebral palsy with a history of perinatal stroke/brain bleed who are US residents.
Statistical Methodology	Adverse event reporting frequency (% of total participants enrolled) and tolerability will be compared to pediatric tDCS studies performed within the laboratory setting and administered by trained research personnel. This data is publicly available in the form of published trials from our group and other groups. For participants in the 6-month/12-month follow-up, we will monitor for any change in motor function by comparing box and blocks scores from the primary study and 6-month/12-month study follow up visits. We will also assess current medical status by pursuing updated medical records.
Estimated Subject Duration	The duration of the study for each subject is approximately 5 days.
Estimated Enrollment Period & Study Duration	Study enrollment and follow-up will occur over 10 months with the total expected duration of the trial to be 12 months.

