10.2.5 Adverse events survey

Tolerance and report of any symptoms will be formally assessed using tDCS-specific participant safety questionnaires. This includes common mild effects like skin tingling and itching, as well as others such

as headache, anxiety and mood changes, or any other events. This survey is filled out before, during at the 10-minute mark, and after tDCS stimulation sessions 1-5.

10.2.6 1-week Follow-up

We will ask the participants an open-ended question to check-in, assess the family's experience with the overall procedure and potential interest in future studies. This will be called the tDCS tolerance survey. This will occur via telephone one week after completion of the session.

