10.8 Safety Oversight

The full details of the planned study monitoring are included in the Data Safety and Monitoring Plan (DSMP).

The PI will oversee the safety of the entire study, including careful assessment and appropriate reporting of all AEs and SAEs. A trained study team member will be present during stimulation to monitor the safety of the participant. The parent/legal guardian or adult participant and study team will report any adverse events, which arise after any session of tDCS or behavioral assessment, to the investigator and the investigator will convey the concerns to the Medical Monitor immediately upon receipt of this information to determine the optimal recommendation for care. The Medical Monitor will review each case after independent analysis of vital signs/symptoms and the occurrence of any minor or SAE. Incorporation of this Medical Monitor review will occur in addition to the safety and risk mitigation plans that we have established during each active session with the child and family. The Medical Monitor will review these reports and determine continuation of study based on comparative analysis of study stopping rules.

The Medical Monitor for this study is:

[name]
Assistant Professor (CHS), Department of Pediatrics
[name]
[contact]

[name] holds board certifications in General Pediatrics, Physical Medicine and Rehabilitation, and Pediatric Rehabilitation Medicine. [name] will utilize this background and her experience evaluating patients with cerebral palsy as the Waisman Center Cerebral Palsy Clinic Director to fulfill the role of Medical Monitor.

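### The available text sets no adverse-event capture criterion for the published laboratory trials, so a home-versus-laboratory difference in mild solicited symptoms may reflect how often children were asked

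*Combined protocol and SAP*

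**What the plan says.** **The comparison.** The Synopsis (section 3.1, Statistical Methodology row) says: "Adverse event reporting frequency (% of total participants enrolled) and tolerability will be compared to pediatric tDCS studies performed within the laboratory setting". On the source of the comparator data it says: "This data is publicly available in the form of published trials from our group and other groups". It limits comparators to pediatric tDCS studies done in the laboratory by trained research staff. It names no study and says nothing about how those studies collected adverse events.

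**Capture at home.** Section 10.2.5 says: "Tolerance and report of any symptoms will be formally assessed using tDCS-specific participant safety questionnaires". On content it says "This includes common mild effects like skin tingling and itching, as well as others such" as headache, anxiety and mood changes, with any other event added. On timing: "This survey is filled out before, during at the 10-minute mark, and after tDCS stimulation sessions 1-5". The study calendar (10.1) and the session descriptions (10.2.1) agree.

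**Role.** The primary endpoint in the Synopsis includes "Adverse events survey (pre, during, and post stimulation on sessions 1-5)", together with the Box and Blocks test.

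**Size and design.** "A total of 10 subjects will be recruited". The trial is open label, with no concurrent laboratory arm.

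**The concern.** The measure is a percentage of participants. A child counts once, however many reports there are, so the figure depends on the number of occasions on which a report could be made. A tingle that is present at 10 minutes and gone at the end is recorded at home. A laboratory trial that asked only after the session, or recorded only volunteered complaints, may miss the same tingle.

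With no concurrent laboratory arm, nothing in the design separates the effect of setting from the effect of asking. If the comparator asked less, home stimulation looks worse than it is. If the comparator asked more, home stimulation looks better than it is. The results are meant to inform a larger study (section 5.3), so a misread contrast could carry forward.

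This is a separate matter from the number of active sessions: the problem remains when the two courses are equally long.

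**Working it through.** The plan gives no comparator rate, margin, test or expected event rate, so there is no figure to reproduce. The check below counts the inquiries and then shows how far the measure can move when only the asking differs.

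**Inputs from the documents**
- Surveys per session: 3 (before, at 10 minutes, after) (10.2.5).
- Sessions: 5, of which 1 is mock, 1 sham and 3 active (8.2, 10.1).
- Participants: 10 (3.1).

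**Counts per child**
- All surveys: 3 × 5 = 15.
- Surveys on active days: 3 × 3 = 9.
- During or after active current: 2 × 3 = 6.
- An after-only schedule over the same three active sessions: 1 × 3 = 3.

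**Assumptions (not in the documents)**
- Chance *p* of a symptom report per survey: 10% or 20%, the same in both settings.
- Within-child correlation *r* of answers: 0.3 or 0.6, with independence (*r* = 0) shown only as the outer limit.
- The comparator asks after the session only, and its question does not recover symptoms that had already passed.

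**Formulas**
- Independent answers: P(any report in *n* surveys) = 1 − (1 − *p*)^*n*.
- Correlated answers (beta-binomial): let *s* = (1 − *r*)/*r* and *b* = (1 − *p*)*s*. Then P(any report) = 1 − the product over *i* = 0 to *n* − 1 of (*b* + *i*)/(*s* + *i*).

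**Worked case, *p* = 10%, *r* = 0.3.** Here *s* = 0.7/0.3 = 2.333 and *b* = 0.9 × 2.333 = 2.1. The six factors are 0.9000, 0.9300, 0.9462, 0.9562, 0.9632 and 0.9682.
- Three surveys: 1 − (0.9000 × 0.9300 × 0.9462) = 20.8%.
- Six surveys: 1 − the product of all six = 29.4%.
- Gap: 8.6 points, with no true difference.

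**All cases, 6 surveys against 3**

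| *p* | *r* | 6 surveys | 3 surveys | Gap (points) |
|---|---|---|---|---|
| 10% | 0.3 | 29.4% | 20.8% | 8.6 |
| 10% | 0.6 | 19.4% | 15.8% | 3.7 |
| 20% | 0.3 | 51.4% | 38.6% | 12.8 |
| 20% | 0.6 | 36.1% | 30.1% | 6.0 |
| 10% | 0 (limit) | 46.9% | 27.1% | 19.8 |
| 20% | 0 (limit) | 73.8% | 48.8% | 25.0 |

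Gaps are taken before rounding. With correlation of 0.3 to 0.6 the range is 3.7 to 12.8 points.

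**If all 15 surveys count.** The Synopsis does not say whether reports before stimulation, or on mock and sham days, enter the percentage. If they do, and *p* is the same at every survey, then at *p* = 10% the home figure against three surveys is 41.0% against 20.8% (*r* = 0.3) or 24.1% against 15.8% (*r* = 0.6).

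**Direction.** The sums are symmetrical. If a comparator asked six times and the home figure rested on three, the same gaps would favor the home setting.

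**Sampling error for scale.** The exact (Clopper-Pearson) 95% interval for 3 of 10 is 6.7% to 65.2%; for 0 of 10 the upper limit is 30.8%.

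**The case against.** **Silence is not permission.** A reader might infer that the plan admits comparators whatever their method of capture. The documents do not say so. The table of contents lists a Study Analysis section (12.1 to 12.5) and adverse-event definition and reporting sections (14.1 to 14.5) whose text is not in the available document: it breaks off in section 10.3.7 and resumes at Unanticipated Problems. A rule could have stood there. This objection stands, and the point is limited to the text that can be read.

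**No decision hangs on the comparison.** A reader might also infer that the contrast carries the primary safety conclusion. That is too strong. The stated safety hypothesis is good tolerance without serious adverse effects (6.1), on which solicited tingling has little bearing. Box and Blocks is part of the primary endpoint. Continuation rests with the Medical Monitor and the stopping rules (10.8, 10.10). No test or margin is attached in this exploratory pilot of 10. All of this stands and lowers the stakes. It does not remove the problem, because the Synopsis still proposes the comparison for all adverse-event reporting and for tolerability.

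**The comparators may have used similar surveys.** This is possible, especially for the group's own trials. The documents do not tell, so neither the presence nor the direction of bias can be established here. If capture did match, the proposed rule would cost almost nothing.

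**The illustration could be too large.** Gaps of 20 to 25 points need independent answers from the same child, which is implausible. A post-session question with a whole-session recall period would shrink the gap further. At 4 to 13 points the gap is about 0.4 to 1.3 children in 10, well inside sampling error. That is fair, but bias and imprecision are different faults: an exact interval does not correct a mismatch in capture.

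**Events reported outside the survey.** Section 10.8 says: "The parent/legal guardian or adult participant and study team will report any adverse events, which arise after any session of tDCS or behavioral assessment". This describes escalation to the Medical Monitor. It is not stated to feed the percentage, so nothing here rests on it.

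**Conclusion.** The point holds in limited form. The available text compares a home percentage built on repeated, solicited questions with published laboratory figures, and it sets no criterion for how those figures were collected. A difference in mild solicited symptoms could therefore come from the asking, in either direction. Serious events are much less affected.

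The illustrative size is about 4 to 13 points with no true difference. It rests on an assumed 10% to 20% chance of a report per survey, within-child correlation of 0.3 to 0.6, and six during-and-after surveys set against three after-only surveys without recall of earlier symptoms. It is larger if all 15 surveys count. None of the assumed rates comes from the documents.

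The text does not show that any actual comparator used lighter capture, or that the home trial will look worse. The change is worth making before the data are summarized, because it is cheap and the comparison cannot be interpreted without it.

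**What to change.** In the Statistical Methodology row of section 3.1 (and in any fuller statistical section, if one exists):

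1. Draw a conclusion of higher or lower frequency only against published trials that used a solicited tDCS symptom questionnaire.
2. For each such trial, compute the home percentage from the active-session survey time points that match its capture window, for example the post-session surveys alone. Match symptom items where the publication reports them.
3. Tabulate each comparator's capture method and number of inquiries per child beside its percentage.
4. List trials with volunteered or unstated capture descriptively, with no statement of relative risk.
5. Show exact intervals for the home percentages.

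**Cost.** Plan wording, and a re-tabulation of surveys already collected by time point. No visit, survey or procedure changes.

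**Downside.** Fewer trials will qualify. Publications may not report participant-level percentages by item and time point, so possibly none can be matched fully. In that case the comparison should be presented as descriptive only.

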3.2 Schematic of Study Design

6 month//12-month
follow up

Optional 6 month/12-month Follow up
 Informed Assent and Consent obtained
 Medical Records Obtained
 In home remote Box and Blocks motor assessment
 GMFCS, Pediatric Cognition, Current Therapy, tDCS tolerance, and tDCS Subject
 Report of Symptoms surveys

5.0 INTRODUCTION

5.1 Cerebral Palsy and Motor Rehabilitation

An estimated 3.6 per 1,000 births in the United States are affected by stroke or brain bleeds which can lead to Cerebral Palsy (CP), a developmental disorder associated with motor impairment^(1,2). While, the majority of rehabilitation approaches focus on behavioral repetition to improve gait and upper extremity function, these therapies can require extensive practice times and extent of recovery is variable. Thus, there is a need for novel strategies which can optimize the speed and consistency of rehabilitation outcomes for this population^(3,4). Brain development during childhood is characterized by heightened neuroplastic potential⁽⁵⁾ stressing the importance for intervention methods that harness neuroplasticity. Accordingly, several therapies (e.g., intensive training of the upper extremities) are theoretically based in mechanisms of motor learning and use-dependent plasticity⁽⁶⁾.

5.2 Investigational Procedure

Non-invasive brain stimulation (NIBS), specifically transcranial direct current stimulation (tDCS), provides an approach for modulation of neuroplasticity that is safe, inexpensive, and portable. Furthermore, rehabilitation approaches combined with tDCS have shown promise to improve motor function recovery and quality of life after stroke in adults⁽⁷⁾. Integrating the application of NIBS may allow for enhanced rehabilitation during the enhanced neuroplastic period of childhood and NIBS has demonstrated promising outcomes in increasing the rate and extent of recovery⁽⁸⁾. The Pediatric Neuromodulation Laboratory has pioneered the development of combined pediatric rehabilitation interventions and tDCS to improve motor function⁽⁹⁻¹¹⁾. Our studies have shown that in children with CP the use of tDCS is safe, feasible, and successful at modifying motor performance when in combination with other physical therapy interventions. tDCS is not currently available to subjects without taking part in the study. In this study, we plan to have a trained study team member instruct administration of tDCS in the remote setting during a synchronous zoom call with another trained study team member at the site of stimulation to monitor safety during sessions with the active device. To ensure the device is safely used in the home setting, and only during designated times, the safety monitor will bring the active device to each stimulation session and remove the device from the home after the session is finished.

5.3 Rationale

Several studies have demonstrated improved effects of rehabilitation interventions when they are combined with tDCS⁽¹²⁾. However, traveling to the laboratory or clinic may increase the difficulty and burden on families to complete an intervention with multiple sessions. This highlights the opportunity for remotely supervised at-home interventions. In adults, telerehabilitation, including integration of tDCS in the at-home environment, has offered the opportunity to improve access, lower the cost, and improve compliance with such treatments that require repetitive practice^(13,14). However, there is further need to explore the feasibility and tolerability in pilot studies for pediatric application, and to expand the investigation in larger randomized controlled clinical trials to assess reproducibility and efficacy⁽¹⁵⁾.

To advance the reach of teleneuromodulation in pediatric rehabilitation it is crucial to extend the safety and accessibility of this affordable intervention. However, prior to the COVID-19 pandemic, there were no studies remotely performing tDCS for *pediatric* populations. During the pandemic Stay-at-Home mandate, we completed a novel feasibility investigation of performing remote *mock* tDCS in children by working with a child-caregiver pair. We found that remote *mock* tDCS is feasible in the home-setting without compromising the efficiency, quality, and comfort of administration. Children and their caregivers were able

to follow remote instructions without compromising the quality of placement and comfort while wearing the tDCS device⁽¹⁶⁾.

With this proposal, we aim to follow-up and build upon our study that demonstrated mock tDCS setup feasibility, to assess ease of use and tolerability of at-home active tDCS in children with CP due to perinatal stroke. Together with gathered feedback about the experiences of children and caregivers during the procedure, knowledge gained will allow us to design a larger scale effectiveness study of a combined teleneuromodulation and rehabilitation intervention for recovery of motor deficits by targeting neuroplasticity and motor skills in pediatrics. Effective remote neuromodulation therapy can provide access to in-person rehabilitation and aid in accommodating mobility and financial challenges. This intervention has the potential to improve motor rehabilitation outcomes and can offer telehealth access, which may reduce treatment cost and improve outcomes when there is limited access to clinic or hospital facilities. Ultimately, this will contribute to a wider reach in improving quality of life across the lifespan in individuals with CP.

